Appendix A International Airline Transportation Association (IATA) 6.2 Guidance Document

Labelling and shipment of biohazard samples

International Airline Transportation Association (IATA) classifies biohazardous agents into 3 categories. For transport purposes the classification of infectious substances according to risk groups was removed from the Dangerous Goods Regulations (DGR) in the 46th edition (2005). Infectious substances are now classified either as Category A, Category B or Exempt. There is no direct relationship between risk groups and categories A and B.

Category A Infectious Substances are infectious substances in a form that, when exposure to it occurs, is capable of causing permanent disability, life-threatening or fatal disease in otherwise healthy humans or animals. Category A pathogens are eg, Ebola, Lassa fever virus:

- Are to be packed and shipped in accordance with IATA Instruction 602.

Category B Infectious Substances are infectious Substances that do not meet the criteria for inclusion in Category A. Category B pathogens are eg, Hepatitis A, B, C, D, and E viruses, Human immunodeficiency virus (HIV) types 1 and 2. They are assigned the following UN number and proper shipping name:

- UN 3373 – Biological Substance, Category B
- are to be packed in accordance with UN3373 and IATA 650

Exempt - all other materials with minimal risk of containing pathogens

- Clinical study samples will fall into Category B or exempt under IATA regulations
- Clinical study samples will routinely be packed and transported at ambient temperature in IATA 650 compliant packaging.
- Biological samples transported in dry ice require additional dangerous goods specification for the dry-ice content.
- IATA compliant courier and packaging materials should be used for packing and transportation and packing should be done by an IATA certified person, as applicable
- Samples routinely transported by road or rail are patient to local regulations which require that they are also packed and transported in a safe and appropriate way to contain any risk of infection or contamination by using approved couriers and packaging / containment materials at all times. The IATA 650 biological sample containment standards are encouraged wherever possible when road or rail transport is used.

Appendix B Guidance Regarding Potential Interactions with Concomitant Medications

The use of any natural/herbal products or other “folk remedies” should be discouraged, but use of these products, as well as use of all vitamins, nutritional supplements, and all other concomitant medications must be recorded in the paper case report form (pCRF).

1. Drugs Inducing CYP3A4 Metabolism that AstraZeneca Strongly Recommend are Not Combined with Osimertinib

Osimertinib is metabolised by CYP3A4 and CYP3A5 enzymes.

A drug-drug interaction study of osimertinib evaluated in patients showed that there is potential for osimertinib being a victim when co-administered with strong inducers of CYP3A4 (osimertinib concentrations are decreased when co-dosed with rifampicin).

The following potent inducers of CYP3A4 must not be used during this study for any patient receiving osimertinib.

Table C1 Drugs Inducing CYP3A4

Contraindicated drugs	Withdrawal period prior to osimertinib start
Carbamazepine, phenobarbital, phenytoin, rifampicin, rifabutin, rifapentine	3 weeks
St John's Wort	
Phenobarbitone	5 weeks

This list is not intended to be exhaustive, and a similar restriction will apply to other agents that are known to strongly modulate CYP3A4 activity. Appropriate medical judgment is required. Please contact AstraZeneca with any queries you have on this issue.

2. Medicines Whose Exposures may be Affected by Osimertinib that AstraZeneca Considers may be Allowed with Caution

Osimertinib may increase the concentration of sensitive BCRP and Pgp substrates (concentration of the sensitive BCRP substrate, rosuvastatin and sensitive Pgp substrate, fexofenadine, are increased).

Table C2 Exposure, Pharmacological Action and Toxicity may be Increased by Osimertinib

Warning of possible interaction	Advice
Rosuvastatin	Drugs are permitted but caution should be exercised and patients monitored closely for possible drug interactions. Please refer to full prescribing information for all drugs prior to coadministration with osimertinib.
Sulfasalazine	
Doxorubicin	
Daunorubicin	
Topotecan	
Dabigatran	
Aliskiren	
Digoxin	

3. Drugs that may Prolong QT Interval

The drugs listed in this section are taken from information provided by the Arizona Center for Education and Research on Therapeutics on the CredibleMeds® website <https://www.crediblemeds.org/>. The website categorizes drugs based on the risk of inducing Torsade de Pointes (TdP).

During screening the drugs that patients are currently receiving (prescription and nonprescription) should be checked opposite the ArizonaCert website. In addition, drugs intended for use following study treatment initiation should be checked opposite the website.

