3.2 Exclusion criteria

Patients should not enter the study if any of the following exclusion criteria are fulfilled:

1. Involvement in the planning and/or conduct of the study (applies to both AstraZeneca staff and/or staff at the study centre).
2. Participation in another clinical study with an IP during the previous 14 days (or a longer period, depending on the defined characteristics of the agents used).
3. Treatment with any of the following:
 - Treatment with an EGFR-TKI (erlotinib, gefitinib or afatinib) within 10 days or at least 5x the half-life, whichever is the longer, of the first administration of IP. If sufficient washout time has not occurred due to schedule or PK properties, an alternative appropriate washout time based on known duration and time to reversibility of IP related AEs could be agreed upon by AstraZeneca and the Investigator.
 - Any cytotoxic chemotherapy, investigational agents or other anticancer drugs from a previous treatment regimen or clinical study within 14 days of the first administration of the IP.
 - Osimertinib in the present study (ie, administration with osimertinib previously initiated in this study) or other studies. Patients who were enrolled, screened but not dosed (ie, withdrew from the study prior to dosing) may be re-enrolled and rescreened if in the opinion of the Investigator, the reason(s) for earlier withdrawal no longer applies.
 - Major surgery (excluding placement of vascular access) within 4 weeks of the first administration of the IP.
 - Radiotherapy (including brain) with a limited field of radiation within 1 week of the first administration of the IP, with the exception of patients receiving radiation to

- more than 30% of the bone marrow or with a wide field of radiation which must be completed within 4 weeks of the first administration of the IP.
- Patients currently receiving (or unable to stop use at least 3 weeks before receiving the first administration of osimertinib) medications or herbal supplements known to be potent inducers of CYP3A4 (see Appendix B).

4. Any unresolved toxicities from prior therapy greater than the Common Terminology Criteria for Adverse Events (CTCAE) grade 1 at the time of starting the IP with the exception of alopecia and grade 2, prior platinum therapy-related neuropathy.
5. History of brain surgery or major brain trauma in the last year (if the surgery is in the same hemisphere as the brain metastasis).

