3.5 Methods for assigning treatment groups (Not applicable)

3.6 Methods for ensuring blinding (Not applicable)

3.7 Methods for unblinding (Not applicable)

3.8 Restrictions

The following restrictions apply while the patient is receiving the IP and for the specified times before and after:

1. Females of child-bearing potential should use reliable methods of contraception from the time of screening until 6 weeks after discontinuing study treatment. Acceptable methods are provided in Appendix C (Definition of Women of Childbearing Potential and Acceptable Contraceptive Methods).
2. Male patients should be asked to use barrier contraceptives (ie, by use of condoms) during sex with all partners during the trial and for a washout period of 4 months. Male patients should avoid procreation for 4 months after completion of trial treatment. Patients should refrain from donating sperm from the start of dosing until 4 months after discontinuing study treatment.
3. Once enrolled all patients must try to avoid concomitant use of medications, herbal supplements and/or ingestion of foods that are known to be potent inducers of CYP3A4 whenever feasible, but patients may receive any medication that is clinically indicated for treatment of AE. Such drugs must have been discontinued for an appropriate period before they enter screening and for a period of 3 months after the last administration of osimertinib. All concomitant medications should be captured on the paper case report form (pCRF). Guidance on medicines to avoid, medications that require close monitoring and on washout periods is provided (see Appendix B “Guidance regarding Potential Interactions with Concomitant Medications”).
4. If medically feasible, patients taking regular medication, with the exception of strong inducers of CYP3A4 (see Appendix B), should be maintained on their regular medication throughout the study period. Patients taking concomitant

medications whose disposition is dependent upon the Breast Cancer Resistance Protein (BCRP) and/or P-glycoprotein (P-gp) with a narrow therapeutic index should be closely monitored for signs of changed tolerability as a result of increased exposure of the concomitant medication whilst receiving Osimertinib. Guidance on medications to avoid, medications that require close monitoring and on washout periods is provided (see Appendix B “Guidance regarding Potential Interactions with Concomitant Medications”).

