7.7.1 Other concomitant treatment

Medication other than that described in Appendix B, which are considered necessary for the patient's safety and wellbeing, may be given at the discretion of the Investigator and recorded in the appropriate sections of the pCRF.

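### Section 3.8 tolerates potent CYP3A4 inducers that Appendix B forbids, and the flat 3-week washout in exclusion 3 falls short of the 5-week row in Table C1

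*Protocol*

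**What the plan says.** **On-study use.** Protocol Section 3.8 item 3 reads "Once enrolled all patients must try to avoid concomitant use of medications, herbal supplements and/or ingestion of foods" that are potent CYP3A4 inducers, "whenever feasible, but patients may receive any medication that is clinically indicated for treatment of AE". Item 4 of the same section keeps patients on their regular medication but excepts strong CYP3A4 inducers, with a pointer to Appendix B. Section 7.7.1 gives the investigator discretion over "Medication other than that described in Appendix B, which are considered necessary".

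Appendix B (the interaction guidance) is firmer in its text: "The following potent inducers of CYP3A4 must not be used during this study for any patient receiving osimertinib". Table C1 labels the listed drugs as contraindicated, and the appendix extends a similar restriction to other strong modulators of CYP3A4. Its heading is softer: "Drugs Inducing CYP3A4 Metabolism that AstraZeneca Strongly Recommend are Not Combined with Osimertinib".

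**Washout.** Section 3.8 item 3 says "Such drugs must have been discontinued for an appropriate period before they enter screening", gives no length, and adds "Guidance on medicines to avoid, medications that require close monitoring and on washout periods is provided", with a reference to Appendix B. Exclusion criterion 3 (Section 3.2) excludes patients currently receiving potent inducers or "unable to stop use at least 3 weeks before receiving the first administration of osimertinib". Table C1 also counts back from the start of osimertinib. It gives 3 weeks for a group that includes phenobarbital and, in a separate row, 5 weeks for phenobarbitone.

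**The concern.** An investigator who follows Section 3.8 item 3 literally may give a listed inducer when avoidance is judged not feasible, or to treat an adverse event. Appendix B contraindicates the same drug because an interaction study with rifampicin showed lower osimertinib concentrations. What is at stake is the patient's exposure to active cancer treatment. The stake extends into the continued access phase, because Section 9.3 ends the study only when the last patient has left that phase.

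The washout text raises a second problem. An investigator who applies exclusion 3 exactly as written can enrol a patient whom Table C1 says should have stopped the drug earlier. In both cases one section of the protocol permits what another forbids, so this is a conflicting rule and not merely missing detail.

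**Working it through.** The plan gives no figure of its own to reproduce. The check is a comparison of text with some day counting.

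**Step 1: strength of the rule.**

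| Place | Rule on strong inducers | Exception |
|---|---|---|
| Section 3.8 item 3 | try to avoid, where feasible | any drug indicated for an adverse event |
| Section 3.8 item 4 | not among regular medication to be maintained | none for strong inducers |
| Section 7.7.1 | outside investigator discretion if in Appendix B | none |
| Appendix B, text and Table C1 | banned, contraindicated | none |
| Appendix B, heading | strongly advised against | not stated |

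The adverse-event clause does not reconcile item 3 with Appendix B, because the feasibility qualifier softens all use. Appendix B shows how the sponsor writes an exception when one is meant: its part on drugs with a known torsades risk allows co-administration when essential for patient management. The part on inducers has no such clause.

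**Step 2: length of washout.** Let d be the number of days from stopping the drug to the start of osimertinib.

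- Exclusion 3: d ≥ 3 × 7 = 21.
- Table C1, phenobarbital: d ≥ 21.
- Table C1, phenobarbitone: d ≥ 5 × 7 = 35.

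For phenobarbitone, any d from 21 to 34 passes exclusion 3 and breaches Table C1, a band of 35 − 21 = 14 days. This holds whether or not the two names mean one drug. If they do, Table C1 also contradicts itself by the same 14 days.

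**Step 3: end point of the count.** Section 3.8 counts to screening entry; exclusion 3 and Table C1 count to the start of osimertinib. Table 1 puts screening at Day −28 to Day −1. Osimertinib tablets start on the day of PET2. With no Day 0, Day −k is k days before Day 1. A patient who enters screening and stops an inducer on Day −28 has, before the first tablet:

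- PET2 on Day 2: 28 + 1 = 29 days
- PET2 on Day 7 (the limit if Table 1 footnote c is counted from PET1): 28 + 6 = 34 days
- PET2 on Day 8 (the limit in Section 7.2): 28 + 7 = 35 days

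The same patient has 0 days before screening entry. The 21-day period is met in every case. A 35-day period is met only with PET2 on Day 8.

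**Step 4: use in the analysis.** SAP 3.2 lists receipt of a prohibited concomitant medication among events that may affect PK evaluation, and leaves inclusion to the PK scientist. SAP 4.3.1 sorts medications as allowed or disallowed from protocol Appendix C, the letter that the protocol's table of contents gives to the interaction guidance. Neither relies on Section 3.8.

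**The case against.** The best defence is that the protocol, read as a whole, already has one rule. Section 3.8 item 4, Section 7.7.1 and Appendix B point the same way, and item 3 itself sends the reader to Appendix B. That is right about intent, and it is why item 3 should be the text to change. It does not make item 3 consistent: the sentence still permits use that the appendix forbids.

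On washout, one can say that exclusion 3 also refers to Appendix B and that its 3 weeks is only a minimum. The criterion nevertheless states a single length, and a patient 25 days off phenobarbitone is not excluded by its words.

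Several stronger readings are tempting but not supported:

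- *Results are compromised.* Nothing shows that any PK, PET or safety summary would change. The PK scientist's decision under SAP 3.2 already covers affected PK data, and the number of inducer users is unknown.
- *The SAP classification is undefined.* SAP 4.3.1 works from the appendix, so the soft wording in Section 3.8 cannot alter that table.
- *There are two competing eligibility tests for the end point.* Eligibility is set mainly by Sections 3.1 and 3.2, where exclusion 3 agrees with Table C1. Section 3.8 reaches eligibility only through the general undertaking in inclusion 11 to keep to study restrictions.
- *Exclusion 3 is ambiguous between current use and use that can be stopped.* Table 1 checks the criteria at screening and again at PET1, and the bracketed text reads as an ordinary washout rule.

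One counter-argument deserves weight. The screening end point in Section 3.8 is the only text that places washout before PET1. Under the osimertinib-start end point, a patient with exactly 21 days off is 20 days off at PET1 (PET2 on Day 2) or 14 days off (PET2 on Day 8). Exclusion 3 and Table C1 already allow this, and the documents do not show that it affects PET1.

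**Conclusion.** The protocol is wrong as written on two points and untidy on a third; overall the finding is minor. Section 3.8 item 3 conflicts with the ban in Appendix B. The flat 3 weeks in exclusion 3 conflicts with the 5-week row of Table C1, over a 14-day band (21 to 34 days off the drug). The screening end point in Section 3.8 is a stray phrase at odds with the two places that do state a length.

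The first two conclusions rest on the text alone. The day counts in Step 3 assume that the start of osimertinib means the first oral dose. SAP 3.3 also speaks of IV dosing of osimertinib. Counted to the Day 1 microdose, Day −28 gives 28 days and a 35-day washout never fits within screening. That phenobarbital and phenobarbitone are one drug is an assumption which the documents do not state. Only the claim that Table C1 contradicts itself depends on it.

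**What to change.** 1. **Section 3.8 item 3.** State that patients must not use strong CYP3A4 inducers (Table C1 and similar agents) while receiving osimertinib. Limit the adverse-event clause to medications other than these, and direct the investigator to contact the AstraZeneca physician if one seems unavoidable. Bring the Appendix B heading into line with its text.
2. **Exclusion 3.** Require at least 3 weeks, or longer if Table C1 says so, before the first administration of osimertinib. Ask the sponsor whether phenobarbital and phenobarbitone are one drug; if so, keep one row with one period.
3. **Section 3.8 washout phrase.** Replace it with a reference to the Table C1 period before the start of osimertinib.

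The conflict does not by itself justify an automatic hold of osimertinib when an inducer is given, or a default of 5 weeks for phenobarbital. Both are clinical choices for the sponsor. The SAP stays as it is.

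The cost is a protocol wording change with no new visits or data. A patient on a 5-week drug must have stopped it by Day −34 if PET2 is on Day 2, by Day −29 if on Day 7, or by Day −28 if on Day 8. Only the last falls inside the screening window, so such a patient will usually need to stop before screening or will not be enrolled.

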3.1 Drugs with a known risk of Torsades de Pointes

Drugs in this category are known to prolong the QT interval and are clearly associated with a known risk of TdP, even when taken as recommended

3.1.1 Before commencing study treatment

Drugs in the category of known risk of TdP must have been discontinued prior to the start of administration of study treatment in accordance with guidance provided in Table C3.

3.1.2 During study treatment

It is recommended that drugs in the category of known risk of TdP are not co-administered with study treatment (osimertinib) and for a period of two weeks after discontinuing study treatment, however if it is considered essential for patient management to co-administer these drugs with study treatment (osimertinib) close monitoring with ECGs and electrolytes is recommended.

The list of drugs may not be exhaustive and is subject to change as new information becomes available. As such investigators are recommended to search the CredibleMeds® website (<https://www.crediblemeds.org/>) to provide the most up to date information.

Table C3 Drugs with a known risk of TdP^a

Contraindicated drug	Withdrawal period prior to osimertinib start
Aclarubicin, Anagrelide, Ciprofloxacin, Clarithromycin, Cocaine, Droperidol, Erythromycin, Levofloxacin, Ondansetron, Papaverine hydrochloride, Procainamide, Sulpiride, Sultopride, Terfenadine Terlipressin	2 days
Cilostazol, Cisapride, Disopyramide, Dofetilide, Domperidone, Flecainide, Gatifloxacin, Grepafloxacin, Ibutilide, Moxifloxacin, Oxaliplatin, Propofol, Quinidine, Roxithromycin, Sevoflurane, Sotalol, Sparfloxacin, Thioridazine	7 days
Azithromycin, Bepridil, Citalopram, Chlorpromazine, Dronedarone, escitalopram, Fluconazole, Halofantrine, Haloperidol, Levomepromazine, Levosulpiride, Mesoridazine	14 days
Donepezil, Terodiline	3 weeks
Levomethadyl, Methadone, Pimozide	4 weeks
Arsenic trioxide ^b , Ibogaine	6 weeks
Pentamidine	8 weeks
Astemizole, Probucon, Vandetanib	4 months
Amiodarone, Chloroquine	1 year

^a This list should be checked against the full and most current list presented in the CredibleMeds® website (<https://www.crediblemeds.org/>)

^b Estimated value as pharmacokinetics of arsenic trioxide has not been studied

3.2 Other TdP risk Categories

Patients receiving drugs that prolong QT interval or may increase the risk of TdP from other TdP risk categories can be enrolled, notwithstanding other exclusions and restrictions, if these drugs are considered essential for patient management and the patient has been stable on therapy. Close monitoring with ECGs and electrolytes is recommended.

Patients with congenital long QT syndrome (CLQTS) are excluded from this study.

3.3 Guidance regardless of TdP risk category

During study treatment and for a period of two weeks after discontinuing study treatment if it is considered essential for patient management to co-administer drugs known to prolong QTc interval, regardless of TdP risk category, close monitoring with ECGs and electrolytes is recommended.

Appendix C Definition of Women of Childbearing Potential and Acceptable Contraceptive Methods.

Definition of Women of Childbearing Potential

Women of Childbearing Potential (WoCBP):

Women between menarche and menopause who have not been permanently or surgically sterilised and are capable of procreation.

Women NOT of Childbearing Potential:

Women who are permanently or surgically sterilised or post-menopausal (definitions below):

Permanent sterilisation includes hysterectomy and/or bilateral oophorectomy and/or bilateral salpingectomy but excludes bilateral tubal occlusion. Tubal occlusion is considered a highly effective method of birth control but does not absolutely exclude possibility of pregnancy. (The term occlusion refers to both occluding and ligating techniques that do not physically remove the oviducts).

- Women who have undergone tubal occlusion should be managed on trials as if they are of WoCBP (eg, undergo pregnancy testing etc, as required by the CSP).
- Women will be considered post-menopausal if they are amenorrheic for 12 months without an alternative medical cause. The following age-specific requirements apply:
- Women under 50 years old will be considered post-menopausal if they have been amenorrheic for 12 months or more following cessation of exogenous hormonal treatments and with LH and FSH levels in the post-menopausal range.
- Women over 50 years of age will be considered post-menopausal if they have been amenorrheic for 12 months or more following cessation of all exogenous hormonal treatments.

Acceptable contraception methods

Highly effective method of birth control is defined in Note 3 in ICH Guidance M3 (Nonclinical Safety Studies for the conduct of Human Clinical trials for Pharmaceuticals) as one that results in a low failure rate (eg, less than 1 percent per year) when used consistently and correctly.

Note that women should have been stable on their chosen method of birth control for a minimum of 2 weeks before entering the trial. Generic names and examples of trade names are given. As trade names may vary, investigators should check the generic name of any contraception to ensure suitability.

Acceptable contraception methods are:

- Total sexual abstinence (abstinence must be for the total duration of the trial and the follow-up period).
- Vasectomised sexual partner plus male condom (with participant assurance that partner received post-vasectomy confirmation of azoospermia).
- Tubal occlusion plus male condom
- Intra-uterine Device (IUD) - provided coils are copper-banded, plus male condom
Intra-uterine system (IUS) Levonorgestrel Intra Uterine System (eg, Mirena), plus male condom.
- Medroxyprogesterone injections (Depo-Provera) plus male condom.
- Etonogestrel implants (eg, Implanon, Norplan) plus male condom.
- Normal and low dose combined oral contraceptive pills, plus male condom.
- Norelgestromin/ethinylestradiol transdermal system plus male condom
- Intravaginal device (eg, ethinylestradiol and etonogestrel) plus male condom.
- Cerazette (desogestrel) plus male condom. Cerazette is currently the only highly efficacious progesterone based pill.

Unacceptable contraception methods

The following methods are considered not to be highly effective and are therefore not acceptable contraceptive methods in AstraZeneca clinical trials:

- Triphasic combined oral contraceptives (COCs)
- All progesterone only pills except, Cerazette
- All barrier methods, if intended to be used alone
- Non-copper containing Intra-Uterine Devices (IUDs)
- Fertility awareness methods
- Coitus interruptus

